9.2.2 Continuous Endpoints

For continuous efficacy endpoints where Mixed-Effect Model Repeat Measurement (MMRM) analysis or Analysis of Covariance (ANCOVA) is performed, missing data will be handled using the following approaches.

- MMRM: The repeat measurement analysis will be conducted using a mixed model including observed measurements at all post-baseline visits up to the end of the analysis period. The mixed model includes the categorical fixed effects of treatment, visit and treatment-by-visit interaction, stratification factors at randomization, and the continuous fixed covariates of baseline measurement. An unstructured variance covariance matrix will be used. If the model cannot converge, an appropriate variance-covariance structure matrix (e.g., autoregressive or compound symmetry) will be used. Parameter estimation is based on the method of restrictive maximum likelihood (REML). MMRM will

be the primary approach in the analysis of continuous variables with repeated measurements.

- ANCOVA: For continuous efficacy variables that are collected at only one post-baseline visit (such as SES-CD), ANCOVA will be used. The model includes the categorical fixed effects of treatment, stratification factors at randomization, and the continuous fixed covariates of baseline and measurement.

9.2.3 Additional Analyses

In addition, As Observed (AO) and tipping point analysis will be performed as supplementary and sensitivity analyses, if appropriate, for categorical or continuous endpoints.

- AO: The AO analysis will not impute values for missing evaluations, and thus a subject who does not have an evaluation on a scheduled visit will be excluded from the AO analysis for that visit. AO will include all values collected in the study.
- Tipping Point Analysis for Binary Endpoints
The tipping point analyses are two-dimensional, i.e., assumptions about the missing outcomes on each of the upadacitinib group and the placebo group can vary independently. The response rate among those subjects with missing response is assumed to be p_0 for placebo group and p_1 for upadacitinib group, and the response rate p_0 and p_1 systematically vary from 0% to 100% by every 10% respectively. Given a set of (p_0, p_1) , the subjects with missing response will be randomly assigned as responders or non-responders using binomial distribution to generate 30 imputed datasets, and the same CMH method used for the primary analysis will be performed on each of the imputed datasets to obtain the results for each comparison between the upadacitinib group versus the placebo group. SAS PROC MIANALYZE will be used to generate the final inferences of the risk difference between upadacitinib group and placebo group, using Rubin's rule.³

If one pair of (p_0, p_1) is found to reverse the study result interpretation in terms of p-value larger than 0.05, then the (p_0, p_1) is identified as the tipping

point. The results for a grid of (p0, p1) combinations are provided in tabular format. Note that missing data 1) on or after the occurrence of the CD-related corticosteroids intercurrent event or 2) on/after the date of initiation of CD-related confounding medications after premature discontinuation of study drug will be considered as non-responders and will not be imputed in the tipping point analysis.

- Tipping Point Analysis for Continuous Endpoints

The tipping point analyses are two-dimensional, i.e., assumptions about the missing outcomes on each of the upadacitinib group and the placebo group can vary independently. In addition, the focus is on scenarios where missing outcomes on upadacitinib are worse than the imputed values on upadacitinib, while missing outcomes on placebo are better than the imputed values on placebo. Missing values are first imputed via MI under MAR assumption, and then a shift parameter is applied to the imputed values (a different shift parameter may be specified for each treatment group). This is implemented by PROC MI using the MNAR statement. The imputation uses a two-step approach, augmentation step using MCMC and imputation step using Monotone Regression. The MNAR statement is applied in the imputation step. The number of imputed datasets is 30.

In cases where the shifted values are smaller than the minimum or larger than the maximum value of the endpoint, (i.e., out of range), the minimum or maximum value of the endpoint is used in further analysis steps. For each pair of shift parameters, the same MMRM/ANCOVA method used for the primary analysis will be performed on each of the imputed datasets to obtain the results for each upadacitinib treatment group versus the placebo group comparison.

These results will be aggregated using Rubin's rule.³

- If a pair of shift parameters is found to reverse the study result interpretation in terms of p-value larger than 0.05, then the pair of shift parameters is identified as the tipping point.

9.3 Co-Primary Efficacy Endpoints and Analyses

9.3.1 Co-Primary Efficacy Endpoints

The co-primary endpoints for the primary analysis of efficacy are:

For EU/EMA regulatory purposes:

- Achievement of clinical remission per PROs at Week 12, and
- Achievement of endoscopic response at Week 12

For US/FDA regulatory purposes:

- Achievement of clinical remission per CDAI at Week 12, and
- Achievement of endoscopic response at Week 12

9.3.2 Primary Analysis of Co-Primary Efficacy Endpoints

The attributes of the estimands corresponding to the co-primary efficacy endpoints are summarized in [Table 1](#).

The co-primary endpoints will be analyzed between upadacitinib group and placebo group using the CMH test, stratified by the randomization factors (baseline steroid use (Yes, No), endoscopic disease severity (SES-CD < 15, \geq 15) and number of prior biologics with prior inadequate response or intolerance (\leq 1, > 1)) based on ITT1.

Table 1. Summary of the Estimand Attributes of the Co-Primary Efficacy Endpoints

Estimand Label	Attributes of the Estimand				Statistical Summary
	Treatment	Endpoint	Population	Intercurrent Events	
Co-Primary 1a	Upadacitinib 45 mg QD vs. placebo	Achievement of clinical remission per PROs at Week 12 (for EU/EMA)	ITT1 population (Subjects who were randomized and received at least one dose of study drug in Part1)	IE1: premature discontinuation of study drug IE2: Initiation or dose escalation of CD-related corticosteroids All data after IE1 will be used until initiation of CD-related confounding medications All subjects will be considered as non-responders at or after IE2	Difference in the proportion of subjects achieving clinical remission per PROs
Co-Primary 1b	Upadacitinib 45 mg QD vs. placebo	Achievement of clinical remission per CDAI at Week 12 (for US/FDA)	ITT1 population (Subjects who were randomized and received at least one dose of study drug in Part1)	IE1: premature discontinuation of study drug IE2: Initiation or dose escalation of CD-related corticosteroids All data after IE1 will be used until initiation of CD-related confounding medications All subjects will be considered as non-responders at or after IE2	Difference in the proportion of subjects achieving clinical remission per CDAI

Table 1. Summary of the Estimand Attributes of the Co-Primary Efficacy Endpoints (Continued)

Estimand Label	Attributes of the Estimand				Statistical Summary
	Treatment	Endpoint	Population	Intercurrent Events	
Co-Primary2	Upadacitinib 45 mg QD vs. placebo	Achievement of endoscopic response at Week 12	ITT1 population (Subjects who were randomized and received at least one dose of study drug in Part1)	IE1: premature discontinuation of study drug IE2: Initiation or dose escalation of CD-related corticosteroids All data after IE1 will be used until initiation of CD-related confounding medications All subjects will be considered as non-responders at or after IE2	Difference in the proportion of subjects achieving endoscopic response

Both of the co-primary efficacy endpoints (EU/EMA: 1a and 2, US/FDA: 1b and 2 as specified in [Table 1](#) above) will be tested at two-sided significance level of 0.05. A CMH based two-sided 95% CI for the difference between treatment groups will be constructed.

The NRI-C approach for handling missing data will be used for main analysis for the co-primary endpoints.

9.3.3 Sensitivity and Supplementary Analyses of the Co-Primary Efficacy Endpoints

Sensitivity analyses of the primary analysis of the co-primary efficacy endpoints are NRI-NC and tipping point analysis.

In addition, sensitivity analyses which are based on "9-2 approach" (as detailed in [Appendix D](#)) to calculate CDAI score and average daily SF/AP will be performed on primary endpoints:

- Achievement of clinical remission per PROs at Week 12 (for EU/EMA regulatory purposes)
- Achievement of clinical remission per CDAI at Week 12 (for US/FDA regulatory purposes)

A supplementary analysis of the co-primary endpoints corresponded to the AO analysis specified in Section 9.2 will be performed in which all data after IE1 and IE2 will be used. CMH analysis as detailed in Section 9.1 will be repeated using AO data handling without any imputation as an additional analysis. The analysis will be conducted on the ITT1 population who have the efficacy measurement at Week 12 visit.

9.3.4 Additional Analyses of the Co-Primary Efficacy Endpoints

NRI-C analysis for the co-primary endpoints will also be conducted on the PP population. In this analysis, subjects with deviations that could potentially impact the analysis of primary endpoint will be excluded. The criteria will be fully defined in the classification plan. Exclusion of subjects will be adjudicated by the therapeutic area medical director (TAMD) and reasons for the subjects to be excluded will be documented and finalized before the Induction Study database lock for the primary analysis. Treatment difference between upadacitinib 45 mg QD and placebo with point estimate and 95% CI will be presented using NRI-C approach with the CMH method as detailed in Section 9.1 and Section 9.2.

9.4 Secondary Efficacy Analyses

9.4.1 Main Analyses of Ranked Secondary Efficacy Endpoints

The attributes of the estimands corresponding to the ranked secondary efficacy endpoints are summarized in [Table 2](#).

In general, continuous secondary efficacy variables with repeated measurements will be analyzed using a MMRM model including factors for treatment group, visit, visit by treatment interaction, and stratification variables. The MMRM analysis is considered primary for inferential purposes. Continuous secondary efficacy variables which are collected at only one post-baseline visit (such as SES-CD) will be analyzed using ANCOVA approach.

Categorical secondary efficacy variables will be analyzed using the CMH test controlling for stratification factors (baseline steroid use (Yes, No), endoscopic disease severity (SES-CD < 15, \geq 15) and number of prior biologics with prior inadequate response or intolerance (\leq 1, > 1)). A CMH based two-sided 95% CI for the difference between treatment groups will be constructed. NRI-C method for missing data will be used for categorical secondary endpoints except occurrence of hospitalizations due to CD during Part 1. The endpoints of "Occurrence of hospitalization due to CD during Part 1" will be analyzed using Chi-square test (or Fisher's exact test if \geq 20% of the cells have expected cell count < 5).

The NRI-C method will be the primary approach for missing data handling for categorical secondary endpoints except hospitalization due to CD during Part 1. The endpoint of "Occurrence of hospitalization due to CD during Part 1" will be analyzed based on the observed data using AO approach only.

Table 2. Summary of the Estimand Attributes of the Key Secondary Efficacy Endpoints

Attributes of the Estimand					
	Treatment	Endpoint	Population	Handling Intercurrent Events	Statistical Summary
Categorical Key Secondary except occurrence of hospitalizations due to CD during Part 1	Upadacitinib 45 mg QD vs. placebo	Achievement of clinical remission per CDAI (EU/EMA) or per PROs (US/FDA) at Week 12, endoscopic remission at Week 12, discontinuation of corticosteroid use for CD and achievement of clinical remission per PROs (EU/EMA) or per CDAI (US/FDA) at Week 12, CR-100 at Week 12, resolution of EIM at Week 12, clinical remission per PROs (EU/EMA) or per CDAI (US/FDA) at Week 4, CR-100 at Week 2	ITT1 population (Subjects who were randomized and received at least one dose of study drug in Part1)	IE1: premature discontinuation of study drug IE2: Initiation or dose escalation of CD-related corticosteroids All data after IE1 will be used until initiation of CD-related confounding medications All subjects will be considered as non-responders at or after IE2	Difference in the proportion of subjects achieving each binary secondary endpoint

Table 2. Summary of the Estimand Attributes of the Key Secondary Efficacy Endpoints (Continued)

Attributes of the Estimand					
	Treatment	Endpoint	Population	Handling Intercurrent Events	Statistical Summary
Occurrence of hospitalizations due to CD during Part 1	Upadacitinib 45 mg QD vs. placebo	Occurrence of hospitalizations due to CD during Part 1	ITT1 population (Subjects who were randomized and received at least one dose of study drug in Part 1)	IE1: premature discontinuation of study drug IE2: Initiation or dose escalation of CD-related corticosteroids All data will be used regardless of IE	Difference in the proportion of subjects with occurrence of hospitalizations due to CD during Part 1
Continuous Key Secondary	Upadacitinib 45 mg QD vs. placebo	Change from Baseline in FACIT-F, IBDQ at Week 12	ITT1 population (Subjects who were randomized and received at least one dose of study drug in Part 1)	IE1: premature discontinuation of study drug IE2: Initiation or dose escalation of CD-related corticosteroids All data after IE1 will be used until initiation of CD-related confounding medications All data after IE2 will not be used for continuous endpoints	Difference in the mean change from Baseline in IBDQ total score and FACIT-F score

9.4.2 Sensitivity and Supplementary Analyses for Key Secondary Efficacy Endpoints

For categorical key secondary endpoints except occurrence of hospitalizations due to CD during Part 1, sensitivity analyses of the of the main analyses of are NRI-NC, and tipping point analysis. NRI-NC and tipping point analysis will be performed for all categorical key secondary endpoints except occurrence of hospitalizations due to CD during Part 1.

For continuous key secondary endpoints, sensitivity analysis of the of the main analysis is tipping point analysis.

A supplementary analysis of categorical key secondary endpoints except occurrence of hospitalizations due to CD during Part 1 corresponded to the AO analysis specified in Section 9.2 will be performed in which all data after IE1 and IE2 will be used. CMH analysis as detailed in Section 9.1 will be repeated using AO data handling without any imputation as an additional analysis. The analyses will be conducted on the ITT1 population who have the efficacy measurement at corresponding visit for the endpoint.

9.5 Additional Efficacy Analyses

Part 1

Other efficacy endpoints will be analyzed similarly as the secondary efficacy endpoints as described in Section 9.4. No multiplicity adjustment will be considered.

Part 2 and Part 3

Only descriptive statistics will be provided for the Part 2 and Part 3 endpoints specified in Section 3.3. The analyses for Part 2 will be performed using ITT2, and the analyses for Part 3 will be performed using the ITT3 by cohort. Categorical endpoints will be summarized by number, percent and two-sided 95% CI; and continuous endpoints will be summarized by n, mean, standard deviation, 95% CI, minimum value, median, and

maximum value; and time to response endpoints will be summarized by n, number of events, and the 25%, 50%, 75% percentiles of time (in days).

A programming error from the ed diary vendor was identified in the total number of daily stools question on patient ed diaries that does not allow the transaction to progress if the answer 0 to question 1, "How many stools in total have you had in the last 24 hours from last record until now?" The vendor has confirmed the issue was only present in languages that are translated from right to left. For this program, that includes Hebrew and Arabic in Israel and Egypt, respectively.

Since data from total stool frequency is only applicable to non-ranked additional efficacy endpoints, a sensitivity analysis will be performed for the additional efficacy endpoint of change from Baseline in average daily total stool frequency at all scheduled visits, by excluding subjects from Egypt and Israel.

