### **Crohn's Disease Activity Index (CDAI)**

Average daily very soft or liquid SF, average daily AP score, and well-being will be calculated from the subject diary. During screening subjects will be instructed on how to calculate the number of very soft and liquid stools, including a visual depiction based on the Bristol Stool Chart. Physical exam and appropriate laboratory values will be calculated at all study visits, except the 30-day follow-up visit, beginning at Baseline. The Screening period will be a minimum of 8 days to calculate the Baseline scores.

The CDAI scores must be calculated using a hematocrit (Hct) value from the same visit laboratory work. The final CDAI for each visit will be calculated once the Hct value is received from the central lab. If the Hct is missing due to technical issues (e.g., lost sample, clotted sample, etc.), the Hct value from the preceding visit may be used.

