#### **Diary Based**

The ePRO data (number of total and liquid or very soft stools, stool consistency per Bristol Stool Chart, use of medications used for endoscopy preparation, if an endoscopy was performed, AP, and general well-being) will be collected electronically via a handheld device into which the subject will record the required pieces of information on a daily basis. The electronic device will be programmed to allow data entry once per day.

All data entered on the device will be immediately stored to the device itself and manually/automatically uploaded to a central server administrated by CRF Health. The investigational site staff will be able to access all uploaded subject entered data via a password protected website, up until the generation, receipt and confirmation of the study archive.

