9.6 Efficacy Subgroup Analyses

To evaluate the consistency of the efficacy over demographic and other baseline characteristics, subgroup analysis will be performed for the co-primary endpoints for the subgroups listed in [Table 3](#) below using ITT1.

For subgroup analysis, point estimate and 95% CI for each treatment group as well as point estimate and 95% CI for treatment differences between upadacitinib group and placebo group will be presented. No p-value will be provided. If, for a subgroup factor except age, sex and race ([Table 3](#)), any of the resulting categories has fewer than 10% of the planned study size, subgroup analyses will not be presented for that category.

Table 3. Subgroups for Efficacy Analysis

Subgroup Factor	Categories
Sex	Male, Female
Age	≤ median, > median
Age	≥ 18 years - < 40 years, ≥ 40 years - < 65 years, ≥ 65 years
Race	White, non-White
Race	White, Black or African American, American Indian or Alaska Native, Native Hawaiian or Other Pacific Islander, Asian, Multiple
Baseline fecal calprotectin	≤ 250 µg/g, > 250 µg/g
Baseline CD-related Steroids Use	Yes, No
Baseline CD-related immunosuppressant use	Yes, No
Baseline CD-related aminosalicylate use	Yes, No
Baseline CD-related antibiotic use	Yes, No
Baseline hs-CRP	≤ 5 mg/L, > 5 mg/L
Baseline CDAI	≤ 300, > 300
Baseline very soft/liquid SF	≤ median, > median
Baseline AP score	≤ median, > median
Baseline SES-CD	< 15, ≥ 15
Crohn's Disease Location at Baseline	Colonic only, Ileal only, Ileal-colonic
Body Weight	≤ median, > median
BMI	Underweight [$< 18.5 \text{ kg/m}^2$], Normal [≥ 18.5 and $< 25 \text{ kg/m}^2$], Overweight [≥ 25 and $< 30 \text{ kg/m}^2$], Obese [$\geq 30 \text{ kg/m}^2$]
Disease Duration	≤ 5 years, > 5 years
Geographic Region	North America, Western Europe, South/Central America, Eastern Europe, Asia, Other
Number of Prior Biologics Failed	≤ 1, > 1
Prior TNF Failure	1, > 1
Prior Ustekinumab Failure	Yes or No
Prior Vedolizumab/Natalizumab Failure	Yes or No

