1. Identify the visit date with CDAI components that are collected, and set it as the CDAI calculation date.
2. Calculate the subtotal scores from the component 1-3 (liquid or very soft stool frequency, abdominal pain score and general well-being) as follows:
 - a. "14-4 approach"
 - i. Select the diary data from 14 days prior to the CDAI calculation date, and set the data from the 4 days (the day prior to, on the day of and two days after the endoscopy date) to missing;
 - ii. Take non-missing diary data from 7 most recent days from step i. If there are multiple entries on the same day for the eDiary component, use the worst result (larger number);
 - iii. If there are non-missing diary data from 7 days, the subtotal score is calculated as the sum of the 7-day scores, and multiplying the factor for the corresponding component as listed in the table above;
 - iv. If there are non-missing diary data from less than 7 days but greater than 3 days (4, 5, 6 days), the subtotal score is calculated as average of the dairy data and times 7, and multiplying the factor for the corresponding component as listed in the table above;
 - v. If there are only less than 4 days of non-missing diary data available, the subtotal score will be set to missing.
 - b. "9-2 approach"
 - i. Select the diary data from 9 days prior to the CDAI calculation date, and set the data from the 2 days (the day prior to, and on the day of the endoscopy date) to missing;
 - ii. Take non-missing diary data from 7 most recent days from step i. If there are multiple entries on the same day for the eDiary component, use the worst result (larger number);

- iii. If there are non-missing diary data from 7 days, the subtotal score is calculated as the sum of the 7-day scores, and multiplying the factor for the corresponding component as listed in the table above;
 - iv. If there are non-missing diary data from less than 7 days but greater than 3 days (4, 5, 6 days) OR from 3 consecutive days, the subtotal score is calculated as average of the dairy data and times 7, and multiplying the factor for the corresponding component as listed in the table above;
 - v. If there are non-missing diary data from 3 non-consecutive days OR less than 3 days of non-missing diary data available, the subtotal score will be set to missing.
- c. Average daily SF/AP will be determined in the same way as described above to derive PROs-related endpoints (for example, clinical remission per PROs);

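### Does the Hebrew/Arabic eDiary fault need sensitivity analyses of the clinical co-primary endpoints as well as of total stool frequency?

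*SAP*

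**What the plan says.** SAP 9.5 describes a vendor programming error in the diary question on total daily stools: the device "does not allow the transaction to progress if the answer 0 to question 1". The vendor confirmed that only right-to-left languages were affected, which in this program means Hebrew in Israel and Arabic in Egypt. The SAP then reasons "Since data from total stool frequency is only applicable to non-ranked additional efficacy endpoints" and plans a single extra analysis, change from Baseline in average daily total stool frequency without subjects from those two countries.

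The Protocol's ePRO section (10.3, Diary Based) lists the contents of the handheld diary: "The ePRO data (number of total and liquid or very soft stools, stool consistency per Bristol Stool Chart", followed by endoscopy items, abdominal pain and general well-being, with one entry allowed per day. Protocol 5.3.1.1 (CDAI) says "Average daily very soft or liquid SF, average daily AP score, and well-being will be calculated from the subject diary".

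SAP Appendix D takes the 7 most recent usable days (the 14-4 approach), averages over 4 to 6 days if fewer are available, and below that: "If there are only less than 4 days of non-missing diary data available, the subtotal score will be set to missing". A score missing for reasons other than COVID-19 counts as non-response under NRI-C (SAP 9.2.1).

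**The concern.** The SAP's argument concerns which endpoints use question 1. It does not address what happened to the remaining questions when the transaction stopped. If the whole day's entry was lost, the loss would depend on the outcome, because only days without any stool are blocked. Appendix D would then average the remaining, worse days, or set the score to missing and make the subject a non-responder.

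The endpoints at stake are remission per PROs and per CDAI at Week 12, remission at Week 4, CR-100 at Weeks 2 and 12, and steroid-free remission.

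The planned analyses would deal with this only in part:

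- The tipping-point analysis lets response rates "systematically vary from 0% to 100% by every 10% respectively" for subjects with a missing response. It leaves alone scores that are present but too high.
- The 9-2 analysis ("Select the diary data from 9 days prior to the CDAI calculation date", less 2 days around endoscopy) keeps about 7 usable days, so it has no spare days to replace blocked ones.
- The region subgroup pools Egypt and Israel with Australia and South Africa as Other (SAP Appendix J). It may not appear at all, because if "any of the resulting categories has fewer than 10% of the planned study size, subgroup analyses will not be presented for that category". Ten percent of 495 is about 50 subjects.

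**Working it through.** **1. What the documents establish.** SAP 9.5 places the fault in the total-stools question. A transaction that will not progress leaves the subject at that question, able to type another number and go on. In that case total stool frequency is wrong, the other items can still be answered correctly, and the SAP's scope is adequate. The one-entry-per-day limit does not show that a blocked day was lost. No passage settles the matter either way, so the rest of this check supposes the unfavourable case.

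**2. Mechanism.** Take 3 zero-stool days and 4 days averaging 3.5 liquid stools.

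- True mean: 4 × 3.5 / 7 = 2.0, which meets the criterion of at most 2.8. CDAI item 1: 2 × 14 = 28.
- Zero days lost and not replaced: mean 3.5, which fails. CDAI item 1: 2 × 7 × 3.5 = 49.

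This is a worst case for the 14-4 rule. With 14 − 4 = 10 usable days, 3 blocked days leave 7, so earlier days take their place. The score becomes missing only when 7 or more of the 10 are blocked.

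**3. Illustrative simulation (assumptions, not document figures).** 200,000 subjects per setting; subject liquid-stool rate gamma with shape 2 and mean 1.5, 2.5 or 4; daily counts Poisson; formed stools Poisson at 0.5, 1.0 or 1.5 per day; days with a total of 0 deleted. The table gives the fall, in percentage points among affected subjects, in the share meeting the stool criterion alone. Missing scores count as failures.

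| Formed stools/day | 14-4 rule (means 1.5, 2.5, 4) | 9-2 rule (means 1.5, 2.5, 4) |
|---|---|---|
| 0.5 | 3.56, 3.01, 2.20 | 10.09, 6.34, 3.86 |
| 1.0 | 0.98, 1.28, 1.14 | 2.89, 2.26, 1.54 |
| 1.5 | 0.54, 0.76, 0.62 | 0.95, 1.00, 0.80 |

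A repeat run with a different seed agreed to within about 0.1 point.

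**4. Scaling to the trial.** The share of subjects in the two countries is not given; 2% to 10% is assumed.

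- 14-4 rule, smallest: 0.02 × 0.54 = 0.01 points. Largest: 0.10 × 3.56 = 0.36 points.
- 9-2 rule, largest: 0.10 × 10.09 = 1.0 point, in a sensitivity analysis.

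**5. Effect on the treatment difference.** Only the gap between the arms' losses matters. Suppose upadacitinib subjects sit at mean 1.5 and placebo subjects at mean 4, with 0.5 formed stools per day. The gap is 3.56 − 2.20 = 1.36 points among affected subjects, or 0.10 × 1.36 = 0.14 points overall, against upadacitinib. The direction is not guaranteed. With 1.0 formed stool per day and means of 1.5 and 2.5, the gap is 0.98 − 1.28 = −0.30, or 0.03 points overall in favour of upadacitinib. The planned differences are 17 points (PROs) and 20 points (CDAI).

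**6. Power.** Inputs from SAP 2.4: 330 vs 165, Fisher's exact test, two-sided 0.05. Exact enumeration reproduces the plan's claim of at least 95%: 99.4% for 29% vs 12% (PROs) and 99.6% for 40% vs 20% (CDAI).

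Extreme bound: 10% of subjects affected, every upadacitinib remitter among them lost, no placebo remitter lost.

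- PROs: 0.29 × 0.90 = 26.1% vs 12%; power 96.4%.
- CDAI: 0.40 × 0.90 = 36% vs 20%; power 96.1%.

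**The case for a change.** The strongest case for a change is one of consistency. The sponsor thought the fault worth a country-exclusion analysis for a non-ranked endpoint, yet gives neither a statement nor a check for co-primary endpoints drawn from the same diary. The 9-2 analysis, added at an agency's request according to SAP 13.0, would be the more exposed of the two scoring rules. One sentence, one table and a few re-runs would cost little.

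It stands that the SAP does not say which items a blocked entry affected, and that no planned analysis corrects a score that is present but biased. The need for more analyses does not follow. If the other items were intact, re-running the diary endpoints without two countries tests nothing. If they were lost, a count of missing diary days by country would show it in ordinary data review. Protocol 5.3.1.1 (Subject Diary) already has site staff review the diary at each visit and take up missing or discrepant entries with the subject. That does not guarantee that blocked days are recovered, but a pattern of missing days would be visible.

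The simulated figures also lean high. PRO remission further requires abdominal pain of at most 1.0 and neither score above Baseline, so some simulated losses would not have been remitters. No endoscopy is scheduled at Weeks 2 and 4, so all 14 days are usable there; the largest fall is then 2.3 points, with at most 0.3 missing. Zero-stool days lost at Baseline precede randomization and should not favour either arm.

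**Conclusion.** No change to the plan is needed. SAP 9.5 leaves out a detail that the vendor or data-management record can supply, and the documents do not show that liquid stool frequency, abdominal pain or well-being was lost. If they were, the expected fall in the stool criterion is about 0.01 to 0.36 points overall under the 14-4 rule. The bias in the treatment difference would be smaller still and probably against upadacitinib. Power stays above 95% in the extreme bound, and endoscopic response does not come from the diary. A misleading efficacy conclusion is therefore not a realistic outcome.

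This rests on three assumptions that the documents cannot confirm: an affected share of no more than 10%, the gamma/Poisson stool model, and the stool criterion standing in for full remission. Abdominal pain and the full CDAI were not simulated. If data review showed that whole diary days were missing in Egypt and Israel, analysts could apply the country exclusion already specified to the clinical endpoints without touching the primary analysis.
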